9.1 Overall Study Design

Single center randomized pilot study

9.2 Study Duration for Subjects

9.2.1 Screening

Following first infertility consultation

9.2.2 Treatment Period

Approximately 2-3 weeks

9.2.3 Unscheduled Visit(s)

N/A

9.2.4 Early Study Termination

N/A

9.2.5 End of Study

July 2020 (anticipated)

10.1 Selection of Study Population

The study will include all consecutive infertile women who attend our center, fulfill the inclusion criteria and consent to participate.

10.2 Inclusion Criteria

The study will include normo-ovulatory patients with the following criteria:

- Age \geq 25 and \leq 40 age
- BMI \leq 35 and \geq 19
- Antimüllerian hormone (AMH) level of \leq 1.5 ng/mL or antral follicular count of \leq 6 follicles or \leq 5 oocytes retrieved in a previous cycle following standard conventional ovarian stimulation.
- Normal basal ultrasound $<$ 6 months before the start of the treatment (presence of uterus and two ovaries without proof of abnormalities)
- Signed informed consent

10.3 Exclusion Criteria

The exclusion criteria will be:

- Testicular sperm extraction
- History of more than three consecutive previous unsuccessful IVF/ICSI cycles
- Use of oral contraceptives $<$ 3 months before start of the treatment
- PCOS according to the Rotterdam criteria
- Ovarian stimulation for pre-implantation genetic testing (PGT-A/M)
- Medical/social freezing
- History of untreated autoimmune, endocrine or metabolic disorders,
- Ovarian cystectomy or oophorectomy
- Patients will be allowed to participate in the study only once.

10.4 Contraception/Pregnancy Avoidance

N/A

11.1 Screening and Enrollment

A responsible investigator will identify potential eligible women for this study. They will be screened and documented as eligible submitted to inclusion criteria. The investigator will obtain informed consents for participation in the study using local IRB approved informed consent forms. Consent will be obtained at the follow up consultation

11.2 Randomization

This is a prospective superiority randomized pilot study. Patients will be randomized to either control group (Group A) or double trigger group (Group B), on the day of triggering, only after patient eligibility has been established and patient consent has been obtained. Randomization sequence and allocation will be created using a computer-generated randomization list, using 1:1 allocation.

11.3 Blinding Procedures

Clinicians who will perform the oocyte retrievals and embryologists will be blinded.

12. Interventions/Treatment

12.1 Treatments Administered

A single injection of 150mcg of corifollitropin alfa will be administrated at day 2/3 of the cycle, followed by 225IU of recombinant FSH (rFSH) in a fixed antagonist protocol. Cycle monitoring will be performed through serum estradiol (E2), progesterone and luteinizing hormone (LH) assessments, and serial transvaginal ultrasound examinations. The study will include exclusively patients with ≤ 9 follicles ≥ 11 mm on the day of triggering. Therefore, patients will be randomly allocated in two groups: Group A (control group) will undergo conventional triggering with hCG 5000 IU and a single oocyte retrieval (OR) will be performed 36 hours later; Group B (study group) will undergo triggering with GnRHa 0,2ml and a first OR will be performed 36 hours later. In both groups, triggering will be performed if two or more follicles ≥ 17 mm are observed and all follicles >10 mm will be aspirated, in line with current clinical practice (Nivet et al., 2016). In Group B (study group), 225 IU of rFSH will continue after the first trigger. Antagonist administration will be initiated when at least one follicle measuring ≥ 14 mm will be present in the ultrasound. If one or more follicles ≥ 17 mm are observed, patients will undergo a second triggering with hCG 5000 IU and a second OR will be performed. In case of patients with no follicular development following 13 additional days of rFSH, the cycle will be cancelled. Metaphase II (MII) oocytes will then be injected according to standard ICSI procedure. In the control group a fresh single/double embryo transfer will be performed

according to clinical practice (day 3 or day 5). For the study group, a freeze-all strategy will be applied, followed by a transfer of a maximum two embryos in an artificially prepared frozen-thawed cycle (overview of all procedures: tables and figures, fig.2).

12.2 Product characteristics

Elonva (corifollitropin alfa) 150 µg

Each pre-filled syringe contains 150 micrograms of corifollitropin alfa in 0.5 mL solution for injection. Elonva is indicated for Controlled Ovarian Stimulation (COS) in combination with a Gonadotropin Releasing Hormone (GnRH) antagonist for the development of multiple follicles in women participating in an Assisted Reproductive Technology (ART) program

Puregon (follitropine beta) 225 IU

One vial contains 225 IU of Puregon. The solution for injection contains the active substance follitropin beta. Puregon is indicated for the treatment of female infertility in the following clinical situations:

- Anovulation (including polycystic ovarian syndrome, PCOS) in women who have been unresponsive to treatment with clomifene citrate.
- Controlled ovarian hyperstimulation to induce the development of multiple follicles in medically assisted reproduction programs [e.g. in vitro fertilisation/embryo transfer (IVF/ET), gamete intra-fallopian transfer (GIFT) and intracytoplasmic sperm injection (ICSI)].

12.3 Randomization and Stratification

Patients will be randomized to either control group (Group A) or double trigger group (Group B), on the day of triggering, only after patient eligibility has been established and patient consent has been obtained. Only patients with ≤ 9 follicles of ≥ 11 mm will be included. Randomization sequence and allocation will be created using a computer generated randomization list, using 1:1 allocation.

12.4 Direction of Administration

Elonva (corifollitropine alfa) and Puregon (follitropine beta)

To prevent painful injections and minimize leakage from the injection site the medication should be slowly administered subcutaneously (or intramuscularly). The subcutaneous injection site should be alternated to prevent lipoatrophy. Any unused solution should be discarded.

Subcutaneous injections may be carried out by patient or partner, provided that proper instructions are given by the physician. Self-administration should only be performed by patients who are well-motivated, adequately trained and with access to expert advice.

12.5 Dosing Regimen

Dosage of Elonva (corifollitropine alfa) is 150 µg and is fixed. Puregon (follitropine beta) 225 IU is started after the first week of stimulation.

12.6 Treatment Compliance

Self-administration will be performed after adequate training of the patient.

12.7 Known Undesirable Effects of Study Drug

Elonva® and Puregon® have the following side effects:

OHSS (ovarian hyperstimulation syndrome)

OHSS is a medical event distinct from uncomplicated ovarian enlargement. Clinical signs and symptoms of mild and moderate OHSS are abdominal pain, nausea, diarrhoea, mild to moderate enlargement of ovaries and ovarian cysts. Severe OHSS may be life-threatening. Clinical signs and symptoms of severe OHSS are large ovarian cysts, acute abdominal pain, ascites, pleural effusion, hydrothorax, dyspnoea, oliguria, haematological abnormalities and weight gain. In rare instances, venous or arterial thromboembolism may occur in association with OHSS. Transient liver function test abnormalities suggestive of hepatic dysfunction with or without morphologic changes on liver biopsy have also been reported in association with OHSS.

Women with known risk factors for a high ovarian response may be especially prone to the development of OHSS during or following treatment with Puregeon. For women having their first cycle of ovarian stimulation, for whom risk factors are only partially known, close observation for early signs and symptoms of OHSS is recommended.

To reduce the risk of OHSS, ultrasonographic assessments of follicular development should be performed prior to treatment and at regular intervals during treatment. The concurrent determination of serum oestradiol levels may also be useful. In ART there is an increased risk of OHSS with 18 or more follicles of 11 mm or more in diameter. When there are 30 or more follicles in total it is advised to withhold hCG administration.

The chance of having a side effect is described by the following categories:

Common (may affect up to 1 in 10 women)

- Ovarian hyperstimulation syndrome (OHSS)
- Pelvic pain
- Feeling sick (nausea)
- Headache
- Tiredness (fatigue)
- Pelvic discomfort

Uncommon (may affect up to 1 in 100 women)

- Ovarian torsion (twisting of the ovary resulting in extreme lower stomach pain)
- Liver enzyme increases
- Miscarriage
- Pain after oocyte retrieval
- Procedural pain
- Releasing an egg too early (premature ovulation)
- Abdominal distension
- Vomiting
- Diarrhoea
- Constipation
- Back pain
- Breast pain
- Bruising or pain at the injection site
- Irritability
- Mood swings
- Dizziness
- Hot flush

Not known (cannot be estimated from available data)

- Allergic reactions (hypersensitivity reactions, both local and generalized, including rash).
- Pregnancy outside the uterus (an ectopic pregnancy) and multiple pregnancies have also been reported. These side effects are not considered to be related to the use of corifollitropin alfa, but to Assisted Reproductive Technology (ART) or subsequent pregnancy.
- In rare instances, blood clots (thrombosis) that formed inside a blood vessel, broke off, and travelled inside the bloodstream to block another blood vessel (thromboembolism) have been associated with Corifollitropin alfa therapy as with other gonadotropins.

13. Study Assessments and Procedures

13.1 Study Assessments

13.1.1 Screening

A responsible investigator will identify potential eligible women for this study. They will be screened and documented as eligible submitted to inclusion criteria. The investigator will obtain informed consents for participation in the study using local IRB approved informed consent forms.

13.1.2 Baseline

A normal baseline ultrasound (<6 months before starting) has to be available before inclusion in the trial.

Before starting treatment, the hormonal profile will be checked with a blood analysis, performed on day 2 or 3 of the menstrual cycle.

13.1.3 Treatment Period

The duration of the treatment itself will depend on every patient's response. The frequency of further follow-up visits with endocrine monitoring and ultrasound is individualized and is based on the growth of the follicles.

13.1.4 Follow-Up

Follow-up in case of pregnancy will be planned until 7-8 weeks of amenorrhea. From that moment patients are referred to their treating obstetrician. Information on the pregnancy and delivery will be collected once available.

13.1.5 End of Study

46 patients (23 in each group) need to be included.

13.1.6 Laboratory Evaluation

Blood samples

During the course of the treatment, several blood samples will be taken. All of them are collected in order to evaluate the hormonal profile and the response to ovarian stimulation (LH, FSH, E, P). Furthermore, follow-up with hCG will take place 12 days after the embryo transfer (overview of all additional blood samples: tables and figures, fig.2)

Follicular fluid and cumulus cells

In both groups, measurement (mean diameter) of all aspirated follicles will be performed on the day of the first and second OR (for group B). At each OPU, the follicles will be individually aspirated and searched for the presence of COCs. All oocytes will be further cultured separately, therefore allowing individual tracing of the oocyte and its correspondent embryo. The correlation between the follicular size and the embryological/reproductive outcome will be further evaluated. In addition, from each individual follicle two samples will be collected i) follicular fluid (FF) and ii) cumulus cells (CC) from the corresponding COC. The COCs will be individually collected and denuded before ICSI. The CCs obtained after denudation will be individually collected in cryo-vials and labelled with the same identification code as the FF from where the COC was recovered. The FF and CC samples will be kept at -196 or -80°C. Both CC and FF are in the standard procedure not used for the patient and are therefore considered waste material. The CC and FF will be analysed in a later stage.

14. Safety Monitoring and Reporting

14.1 Adverse Events

An AE is any untoward medical occurrence in a patient participating in a trial. It includes:

- Any laboratory abnormality, vital sign or finding from physical or gynaecological examination assessed as clinically significant by the investigator (note: findings from assessments and examinations done during screening are not adverse events, but are recorded as medical history).
- Accidental injuries, reasons for any change in medication (drug and/or dose), reasons for any medical, nursing or pharmacy consultation, or reasons for admission to hospital or surgical procedures.

14.2 Suspected Unexpected Serious Adverse Events (SUSAR)

All adverse drug reactions (ADR) to gonadotropins, whether serious or non-serious, are to be captured in the consultations and investigator must record the ADRs in the ADR Log provided in each patient's consultations with information about:

- Adverse Drug Reaction
- Date and time of onset
- Intensity
- Action taken to

- Other action taken
- Date and time of outcome
- Outcome
- Seriousness criteria if applicable
- Short description of ADR (if not serious)

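### The only stated duty to log events covers reactions to gonadotropins, so other harms of Group B's extra retrieval and GnRH agonist trigger need not be recorded

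*Combined protocol and SAP*

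**What the plan says.** Section 14.1 sets a wide definition: "An AE is any untoward medical occurrence in a patient participating in a trial". It extends to "reasons for any medical, nursing or pharmacy consultation, or reasons for admission to hospital or surgical procedures". It does not say who records such events, where, or for how long.

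The recording instruction comes in section 14.2, under a heading about SUSARs: "All adverse drug reactions (ADR) to gonadotropins, whether serious or non-serious, are to be captured in the consultations". The tool is a log of drug reactions: "investigator must record the ADRs in the ADR Log provided in each patient's consultations".

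Section 12.1 describes the exposures. Group A is triggered with hCG and has one retrieval. For the other arm, "Group B (study group) will undergo triggering with GnRHa 0,2ml and a first OR will be performed 36 hours later". Stimulation then continues and, if follicles reach the stated size, "patients will undergo a second triggering with hCG 5000 IU and a second OR will be performed". Section 17 lists the ovum pick-up among the additional costs of the study, so the extra retrieval is added by the research.

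The endpoint lists (section 2 and section 8.2) contain no safety outcome, and section 15.3 describes no safety analysis. Section 15.2 says that there will be no data safety monitoring board. Section 18 treats missing safety outcomes, like missing efficacy outcomes, as negative.

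**The concern.** The definition and the logging duty have different scopes, and the difference does not fall equally on the two arms. hCG is a gonadotropin, so a reaction to Group A's trigger has to be logged. Group B's first trigger is a GnRH agonist, so a reaction to it does not. The second retrieval is a procedure, and only Group B can have one. Bleeding or infection after it is neither a reaction to a gonadotropin nor among the known effects listed in section 12.7.

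If staff follow the text exactly, the trial could report more MII oocytes in Group B with no apparent added harm, partly because harms of the added procedure were never collected. Section 18 could compound this: if negative means no event, an unlogged complication would be counted as an absence of harm.

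**Working it through.** The point is mainly one of scope, so the first step is to set the exposures against the logging rule.

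| Exposure (section 12.1) | Arm | Within the 14.1 definition? | Must be logged under 14.2? |
|---|---|---|---|
| Reaction to corifollitropin alfa or rFSH, including OHSS | both | yes | yes |
| Reaction to hCG trigger | A; B at second trigger | yes | yes |
| Reaction to GnRH agonist trigger | B only | yes | no |
| Reaction to antagonist | both | yes | no |
| Retrieval pain | both; B may have two retrievals | yes | possibly, as it is a listed effect in 12.7 |
| Bleeding or infection after retrieval | both; B may have two retrievals | yes | no |

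Next, whether another section supplies the missing duty:

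- The objectives and endpoints name no safety outcome.
- The analysis section has no safety comparison.
- Table 1, as it reads in the available text, has no adverse-event row for either group.
- The annual safety report in 14.3.3 relies on new information and on what patients report, and no by-arm table is mentioned.

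None of these is a recording rule.

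The plan gives no safety figure to reproduce. Its one power figure is for the primary endpoint: 23 per group, means 5.4 and 3.4, SD 2, two-sided alpha 0.05. The noncentrality is 2 / (2 × √(2/23)) = 3.39 on 44 degrees of freedom, which gives 91.2% power. This agrees with the stated 90% or more and is not in question.

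For scale, what 23 women per arm can show about harms:

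- **No events seen.** The one-sided 95% upper limit for 0/23 is 1 − 0.05^(1/23) = 12.2%. The two-sided exact limit is 1 − 0.025^(1/23) = 14.8%.
- **Difference between arms.** Against 0/23 in Group A, Fisher's exact test gives p = 0.109 for 4/23 in Group B and p = 0.049 for 5/23. Five events against none are therefore needed for p < 0.05.
- **Chance of seeing any event.** The documents give no complication rate. For assumed per-woman rates of 1%, 2%, 5% and 10%, the chance of at least one event among 23 women is 1 − (1 − p)^23 = 21%, 37%, 69% and 91%. These figures show only how sparse the data would be. They apply equally to 23 women in Group A, and they do not isolate the second retrieval, which not every Group B woman will reach.

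**The case against.** The strongest reply is that the plan's concept of an adverse event is wide enough. Section 14.1 sits in the safety monitoring and reporting chapter, covers admissions and surgical procedures, and contrasts adverse events with screening findings, which go into the medical history. That suggests that adverse events are meant to be recorded as such. The annual safety report is not limited to gonadotropins. The investigational products named in section 2 are Elonva and Puregon, so a SUSAR section confined to reactions to gonadotropins is coherent in itself. The eCRF fields are not in the documents, and staff may in practice log more than 14.2 asks.

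Much of this stands. The defect is a mismatch between a wide definition and a narrow logging duty, and the missing sentence could equally be placed in 14.1. But an implied intention is not an instruction, and no text requires the uncovered events to be logged.

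A reader might infer three stronger things that the documents do not support:

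- **That safety cannot be compared at all.** OHSS and other reactions to corifollitropin alfa, rFSH and hCG are to be logged in both arms, serious or not.
- **That every retrieval harm falls outside the log.** Section 12.7 lists procedural pain and pain after retrieval as known effects of the gonadotropins, so an investigator could log them. Bleeding and infection are the clear omissions.
- **That a second antagonist course in Group B is an established exposure.** The first stimulation is described as "followed by 225IU of recombinant FSH (rFSH) in a fixed antagonist protocol" for both groups. A later sentence says "Antagonist administration will be initiated when at least one follicle measuring ≥ 14 mm will be present in the ultrasound". Its place after the sentence on continued rFSH in Group B makes a second course a reasonable reading, but the text does not state it. The point does not depend on it.

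**Conclusion.** The concern holds as a scope error that affects the arms unequally. Under the stated rule, non-gonadotropin harms of the additional retrieval and reactions to the agonist trigger need not be logged in Group B, while reactions to Group A's hCG trigger must be. What is lost is a comparison of overall safety that includes procedural and non-gonadotropin harms. The comparison of gonadotropin reactions remains.

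The conclusion assumes that 14.2 is followed as written and that no recording rule exists outside the documents. The documents do not allow an estimate of how many events would be missed. Even with complete recording, 23 per arm supports description only: zero events would leave rates up to about 12% possible. The primary MII comparison is unaffected, but a statement that Group B gains oocytes without added harm would lack support. The text should be changed.

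**What to change.** 1. Amend 14.2 so that every adverse event and serious adverse event meeting the 14.1 definition is recorded in both arms, from first study treatment to a stated end of follow-up. Starting at randomisation would be too late, because women are randomised on the day of triggering (sections 11.2 and 12.3) and events during the first stimulation would be missed.
2. For each event, record the attribution to each drug (gonadotropin, GnRH agonist, antagonist) and to each retrieval.
3. Add to section 15.3 a descriptive safety table by arm. It should also show events from randomisation and, in Group B, events by first and second retrieval, with OHSS and retrieval complications as named outcomes.
4. In section 18, state that an unrecorded safety outcome is reported as missing, not as absence of harm.

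The cost is revised wording, a wider event log, slightly more recording work and one more table. No change to treatment, sample size or primary analysis follows.

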14.3 Procedures for Handling Special Situations

14.3.1 Pregnancy

The first blood test that will be performed on day 2 or 3 of the menstrual cycle will also include the hCG in order to detect possible pregnancies before starting the treatment. Patients with a positive pregnancy test will be excluded from the trial.

14.3.2 Overdose Management

Patients that will use more medications than the one suggested will be monitored in their referral centre with blood test and ultrasound; although, there are no specific side effects due to the overdose of these medications

14.3.3 Annual Safety Report

An annual safety report will be prepared with all the new information and the notifications that the patients will provide within the study period.

15. Data Collection and Management

15.1 Data Collection

Data will be collected in a secure and encrypted eCRF created specifically for the trial using Filemaker Pro® version 13 (Filemaker Inc.) hosted on a dedicated server at the *CRG-UZ Brussel*.

15.2 Database Management and Quality Control

The database has inbuilt validation procedures to ensure the correct introduction of data and avoid cases of missing information where such is not applicable. The doctors, study nurses and research assistants collaborating in the trial will be responsible for the data collection. Data will be stored for 10 years.

No data safety monitoring board will be established.

15.3 Statistical Considerations and Data Analysis

Analyses were performed in intent-to-treat fashion and per-protocol. Consequently, in the intention-to-treat analysis, all patients will be included in the final analysis as long as after fulfillment of the inclusion criteria they were randomly allocated to one of the treatment groups, whereas the per-protocol analysis will include only those patients who completed the treatment originally allocated. Continuous data will be presented as mean \pm SD or median [range] and categorical data will be described by number of cases, including numerator and denominator, and percentages, in line with the CONSORT statement (www.consort-statement.org). Categorical data and continuous data that do not show a normal distribution will be analyzed by Pearson's χ^2 test/Fisher exact test or Mann-Whitney's U test as appropriate.

The normality of the distributions will be assessed with Kolmogorov-Smirnov's test and graphical methods. All tests will be two-sided. Differences will be considered as statistically significant if the null hypothesis could be rejected with $>95\%$ confidence ($p<0.05$). All tests will be performed with the STATA version 13.

Power/Sample Size:

Our sample size of 46 patients (23 per group) has a power of at least 90% to detect superiority of the double trigger group (mean 5.4 MII) versus control group (mean 3.4 MII), standard deviation ($SD=2$), using a two-sided, t test, at significance level alpha of 0.05.

16. Ethical Considerations

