7.2 Study Activities

The total duration of the study will be approximately 1.5 years

The duration of treatments is per investigators' judgment.

Number of patients included: A total number of 46 women will be analyzed

8. Study Objectives and endpoints

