8.1 Primary Objective

The primary objective measure will be to compare the total number of metaphase II (MII) oocytes between the two groups.

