16.5 Conflict of Interest

There are no conflicts of interest to declare.

17. Finance and Insurance

If the patient will decide to take part in this study, this will not involve any extra costs for her or her insurer. The additional costs of the study (extra medication for prolonged stimulation, ovum pick-up, additional sampling) will be covered by funding from MSD.

Any participation in a clinical study involves a risk, however small it is. Even if there is no fault, the investigator accepts responsibility for damage caused to the participant (or in the event of death, his/her dependents) and directly or indirectly linked to his/her participation in the study. The sponsor has taken out insurance for this responsibility.

18. Reporting and Dissemination

Missing efficacy and safety outcomes will be considered as negative, regardless of the cause which may justify the lack of said information (e.g. cycle cancelled due to the survival after warming of no embryo or loss to follow-up). These patients will be included in the analysis following the ITT principle.

19. Conflict of interest statement

This study is financially supported by MSD.

None of the other investigators have conflict of interest to declare.

20. Tables and Figures

Fig. 1 study design

[figure not shown]

Table 1: Summarizing table of all investigations and procedures

Group A (control group)

	Day 2 of the cycle	Day 8 of the stimulation	Every 1 or 2 days	Final maturation trigger	Ovum pick-up*	Day 3 or 5 after egg retrieval	12 days after embryo transfer
Informed consent	x						
Inclusion/exclusion criteria	x			x			
Infertility/menstrual/reproductive history	x						
Blood sample for endocrine monitoring (LH, FSH, estradiol, progesteron)	x	x	x		x		
Ultrasound with follicle measurement		x	x				
Embryo transfer						x	
Blood sample for pregnancy hormone (hCG)							x

(*) with collection of follicular fluid and cumulus cells

	Day 2 of the cycle	Day 8 of the stimulation	Every 1 or 2 days	Final maturation trigger	1 st Ovum pick-up* with freezing of all embryos	4 days after first pick-up and 3-4 times after that	2 nd Ovum pick-up* with freezing of all embryos	In the next cycle
Informed consent	x							
Inclusion/exclusion criteria	x			x				
Infertility/menstrual/reproductive history	x							
Blood sample for endocrine monitoring (LH, FSH, estradiol, progesteron)	x	x	x		x	x	x	
Ultrasound with follicle measurement		x	x			x		
Embryo transfer								x

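### Does planning both ITT and per-protocol analyses, with neither ranked and completion undefined, put the superiority conclusion at risk?

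*Combined protocol and SAP*

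**What the plan says.** Section 15.3 states: "Analyses were performed in intent-to-treat fashion and per-protocol". For ITT, "all patients will be included in the final analysis", provided they met the inclusion criteria and were randomised. For the second set, "the per-protocol analysis will include only those patients who completed the treatment originally allocated". No sentence calls either analysis primary or supportive.

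Other sections bear on the choice:

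- Section 7.2: "A total number of 46 women will be analyzed". Section 13.1.5 sets the number to be included at the same 46, 23 in each group.
- Section 18 counts missing efficacy and safety outcomes as negative and adds: "These patients will be included in the analysis following the ITT principle".
- Section 8.1 sets the primary objective, to "compare the total number of metaphase II (MII) oocytes between the two groups".
- Section 11.2 places randomisation on the day of triggering.
- Section 12.1 gives Group A one retrieval. Group B continues stimulation towards a second trigger and retrieval, with this exit: "In case of patients with no follicular development following 13 additional days of rFSH, the cycle will be cancelled". Group B's embryos are all frozen, "followed by a transfer of a maximum two embryos in an artificially prepared frozen-thawed cycle".

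**The concern.** The second wave exists in Group B only and takes place after randomisation. Whether it succeeds is part of the primary outcome, because total MII includes the second retrieval. A per-protocol set that drops failed second waves therefore selects on the outcome, in one arm only, and compares the better part of Group B with all of Group A.

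With two analyses and no ranking, a sponsor whose ITT result missed significance could put the per-protocol result forward. The label also has a consequence: section 8.2 makes a cost-effectiveness analysis depend on superiority of the double trigger group, without saying in which analysis set.

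**Working it through.** **1. The plan's own figure.** Inputs from section 15.3: means 5.4 and 3.4, SD 2, 23 per group, two-sided alpha 0.05. Noncentrality = 2 / (2 × √(1/23 + 1/23)) = 3.39 on 44 degrees of freedom, giving power of 91.2%. The stated figure of at least 90% is reproduced. With 22 per group the power is 89.97%, so 23 is the smallest group size that reaches 90% by the t test. The power statement uses all 46 women and leaves no room for a set that loses any.

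**2. What *completed* could mean under section 12.1.**

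- (a) All planned retrievals were done. A cancelled second wave removes the woman, and this can happen only in Group B.
- (b) The allocated pathway was followed, including its own cancellation branch. Nobody leaves for this reason.
- (c) Embryo transfer was reached. Both arms lose women. Table 1 shows freezing at Group B's first pick-up, so a failed second wave need not prevent transfer.

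**3. Size under (a).** The documents give no failure rate f, so 10%, 20% and 30% are assumed. Suppose the whole difference of 2.0 comes from the second retrieval and failure is independent of first-wave yield. Women who reach the second retrieval then average 2/(1 − f) extra MII.

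| f | Group B women removed (23f) | ITT: (1 − f) × 2/(1 − f) | Per-protocol: 2/(1 − f) |
|---|---|---|---|
| 10% | about 2 | 2.00 | 2.22 |
| 20% | about 5 | 2.00 | 2.50 |
| 30% | about 7 | 2.00 | 2.86 |

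Under (b) the per-protocol difference stays at 2.00. Under (c), simulation with an assumed 30–50% chance that each MII oocyte gives a transferable embryo puts it at 1.80–1.94 with independent failure, and at 1.90–2.17 if failure correlates 0.5 with low first-wave yield. Even the direction of the shift under (c) therefore depends on assumptions outside the documents.

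**4. Chance of a discordant result under (a).** Simulated trials had 23 per arm, f = 20%, a negative binomial first retrieval (mean 3.4, variance 4), a Poisson second retrieval and a pooled t test. Each percentage is the chance of p < 0.05 in favour of Group B.

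| True difference | Correlation of failure with low first-wave yield | ITT | Per-protocol | Per-protocol only |
|---|---|---|---|---|
| 1.0 | 0 | 33.9% | 44.5% | 12.0% |
| 0 | 0 | 2.5% | 2.5% | 0.7% |
| 0 | 0.25 | 2.5% | 4.6% | 2.4% |
| 0 | 0.5 | 2.4% | 7.4% | 5.0% |

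The 12.0% arises where Group B truly is better, so it is not a false-positive rate. The rows with no true difference assume that both arms have the same first-wave yield and that every completed second retrieval gives no MII at all. That is an odd null for a strategy whose added step is that retrieval. With independent failure, per-protocol has no inflation, and allowing either analysis to decide gives 2.5% + 0.7% = 3.2%. Larger inflation needs a correlation that nothing in the documents supports.

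**5. When ITT holds.** ITT stays at 2.00 only if first-retrieval MII are kept when the second wave is cancelled. If the section 18 rule set such a woman's total to 0, Group B's mean would be (1 − f) × (3.4 + 2/(1 − f)) = 5.4 − 3.4f, and the difference 2 − 3.4f: 1.66, 1.32 and 0.98 at 10%, 20% and 30%. That reading is strained. The rule covers missing outcomes, and a first-retrieval count is observed. Its example of a cancelled cycle is one in which no embryo survives warming, which is a transfer cycle and not a second stimulation wave.

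**The case for a change.** The strongest case for a change is that the omission is real and cheap to repair. Nowhere is ITT called primary, and the ITT sentence in section 18 concerns missing outcomes, not the ranking of analyses. One undefined word moves the assumed-case per-protocol estimate from about 1.8 to 2.9 MII, and a later reader could not prove from the text that the choice of deciding analysis was made in advance. A few sentences would settle it without extra patients or data.

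The textual facts stand: there is no label, no definition, and the cancellation branch belongs to Group B alone. Three things reduce their weight. First, the wording that bears on the choice points one way, and nothing ties power, superiority or missing data to per-protocol. Second, section 15.3 commits to both analyses, so a discordant ITT result would be visible in any report that follows the plan; selective promotion of per-protocol is conjecture. Third, a definition that keeps cancelled women in the per-protocol set is debatable, because it makes that set nearly the ITT set and leaves it little to add. Women in either arm can also leave for other reasons, such as withdrawal, so the imbalance describes one mechanism and not the whole set.

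**Conclusion.** No change to the plan follows. This is a gap that analysts fill sensibly: ITT on all randomised women as the main result, total MII summed over the retrievals performed, and per-protocol beside it with its exclusions listed by arm and reason. An analyst who follows the plan as written still reaches a sound main conclusion.

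The exposure is confined to the reading of the per-protocol estimate. Under the least favourable plausible definition it would overstate a true difference of 2.0 by 0.5 MII at an assumed 20% failure rate (2.50 − 2.00). Under another definition it would not move at all. Failure rates, correlations and embryo probabilities are assumptions; the documents supply none, and the written cancellation rule is narrow. The conclusion rests on one condition, that first-retrieval MII count in the total when the second wave is cancelled. This is the ordinary meaning of a total and fits the scope of the section 18 rule.
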